10.1.4 FUTURE USE OF STORED SPECIMENS AND DATA

See also Section 10.1.3, Confidentiality and Privacy and Section 10.1.9, Data Handling and Record Keeping, for further information on future use of study records.

Data collected for this study will be analyzed and stored at Humanetics Corporation. After the study is completed, the de-identified, archived data will be transmitted to and stored at Humanetics Corporation, for use by other researchers including those outside of the study. Permission to transmit data to Humanetics Corporation will be included in the informed consent.

There will be no storage of samples (e.g., whole blood or blood serum) for future new research. Storage of any samples (e.g., whole blood or blood serum) will solely be kept as reserves to be used for reanalysis if necessary. If samples are not used within 2 yrs they will be destroyed.

10.1.6 SAFETY OVERSIGHT

Safety oversight will be the responsibility of the Principal Investigator and the Medical Monitor.

10.1.7 CLINICAL MONITORING

Site monitoring will be conducted to ensure that the rights and well-being of trial participants are protected, that the reported trial data are accurate, complete, and verifiable, and that the conduct of the trial is in compliance with the currently approved protocol/amendment(s), with ICH GCP, and with applicable regulatory requirement(s).

Sponsor will monitor the progress of all clinical investigations being conducted under its IND based on the study specific Monitoring Plan, which shall be prepared by the Sponsor. If Sponsor discovers that a participating investigator is not complying with the signed agreement (Form FDA-1572), the general investigational plan, or other requirements the study Sponsor shall promptly either secure compliance or discontinue the investigator's participation in the investigation.

The Sponsor will review and evaluate the evidence relating to the safety and effectiveness of the drug as it is obtained from the participating investigator. The notification process to the study Sponsor begins with the completion and submission of the appropriate CRFs. Investigators are required to report promptly to the Sponsor any adverse events that may reasonably be regarded as caused by, or probably caused by, the drug. If the adverse event meets the serious adverse event criteria, the investigator is required to report the event to the Sponsor within 24 hours of discovery.

Prompt review of the AE by the study Sponsor will be completed to determine if the AE meets any of the criteria for an AE to be reported to the FDA, Investigators, and/or Institutional Review Boards (IRB). Should an AE be determined by the study Sponsor to meet the criteria for a 7- or 15-day reportable event, the medical monitor will be notified promptly. The medical monitor will assist in writing the IND safety report with the study Sponsor. The Sponsor will submit all necessary reports to FDA regarding information relevant to the safety of the drug.

The study Sponsor will promptly investigate all safety information it receives. Should the Sponsor, in consultation with the Medical Monitor, determine that the investigational drug presents an unreasonable and significant risk to subjects, the study shall be discontinued. In this case, the study Sponsor will notify the FDA, all institutional review boards, and all investigators who have at any time participated in the investigation of the discontinuance and assure the disposition of all stocks of the drug outstanding and furnish FDA with a full report of the Sponsor's actions.

10.1.8 QUALITY ASSURANCE AND QUALITY CONTROL

The clinical site will perform internal quality management of study conduct, data and biological specimen collection, documentation, and completion per its Standard Operating Procedures (SOPs).

Quality control (QC) procedures will be implemented beginning with the data entry system and data QC checks that will be run on the database will be generated. Any missing data or data anomalies will be communicated to the site(s) for clarification/resolution.

Following written SOPs, the monitor(s) will verify that the clinical trial is conducted and data are generated and biological specimens are collected, documented (recorded), and reported in compliance with the protocol, International Conference on Harmonisation Good Clinical Practice (ICH GCP), and

applicable regulatory requirements (e.g., Good Laboratory Practices (GLP), Good Manufacturing Practices (GMP)).

The investigational site will provide direct access to all trial related sites, source data/documents, and reports for the purpose of monitoring and auditing by the Sponsor, and inspection by local and regulatory authorities as appropriate and necessary.

10.1.9 DATA HANDLING AND RECORD KEEPING

10.1.9.1 DATA COLLECTION AND MANAGEMENT RESPONSIBILITIES

Data collection is the responsibility of the clinical trial staff at the site under the supervision of the Principal Investigator. The Principal Investigator is responsible for ensuring the accuracy, completeness, legibility, and timeliness of the data reported.

All source documents should be completed in a neat, legible manner to ensure accurate interpretation of data.

Hardcopies of the study visit worksheets will be provided for use as source document worksheets for recording data for each participant enrolled in the study. Data recorded in the electronic case report form (eCRF) derived from source documents should be consistent with the data recorded on the source documents.

Clinical data (including adverse events (AEs), concomitant medications, and expected adverse reactions data) and clinical laboratory data will be entered into a study specific data capture system, a 21 CFR Part 11-compliant data capture system utilized by the Sponsor. The data system includes password protection and internal quality checks, such as automatic range checks, to identify data that appear inconsistent, incomplete, or inaccurate. Clinical data will be entered directly from the source documents.

10.1.9.2 STUDY RECORDS RETENTION

Study documents should be retained for a minimum of 2 years after the last approval of a marketing application in an International Conference on Harmonisation (ICH) region and until there are no pending or contemplated marketing applications in an ICH region or until at least 2 years have elapsed since the formal discontinuation of clinical development of the study intervention. These documents should be retained for a longer period, however, if required by local regulations. No records will be destroyed without the written consent of the Sponsor, if applicable. It is the responsibility of the Sponsor to inform the investigator when these documents no longer need to be retained.

10.1.10 PROTOCOL DEVIATIONS

A protocol deviation is any noncompliance with the clinical trial protocol, International Conference on Harmonisation Good Clinical Practice (ICH GCP), or Manual of Procedures (MOP) requirements. The noncompliance may be either on the part of the participant, the investigator, or the study site staff. As a result of deviations, corrective actions are to be developed by the site and implemented promptly.

These practices are consistent with ICH GCP:

- 4.5 Compliance with Protocol, sections 4.5.1, 4.5.2, and 4.5.3
- 5.1 Quality Assurance and Quality Control, section 5.1.1
- 5.20 Noncompliance, sections 5.20.1, and 5.20.2.

Compliance with the study protocol and all study procedures will be assessed during each monitoring visit. A protocol deviation for this study is defined as any departure from the protocol whether pre-approved by the Sponsor or unplanned. Protocol deviations may be identified during monitoring visits or by the site either in anticipation of a deviation or upon discovery. The research site should complete a Protocol Deviation CRF and submit it to the Sponsor after review and signature by the investigator. Protocol deviations must be sent to the reviewing Institutional Review Board (IRB) per their policies. The site investigator is responsible for knowing and adhering to the reviewing IRB requirements. Further details about the handling of protocol deviations will be included in the MOP.

As specified in the Study Monitoring Plan, the Sponsor will review protocol deviations by site and overall to determine if there are any trends identified that may affect subject safety, data integrity and the impact on analysis and to determine if any actions need to be taken prevent continued deviations.

10.1.11 PUBLICATION AND DATA SHARING POLICY

Publication of clinical trial results will be consistent with the Sponsor's Publication Policy. The first publication in journal, or presentation at a congress, will be based on the consolidated data, analyzed as stipulated by the protocol and agreed upon by investigators.

The Sponsor intends to share all applicable data collected as part of this project with the DoD and the general scientific community. The data will be made as widely and freely available as possible through presentation at scientific conferences and publication of primary data in a peer-reviewed journal.

10.1.12 CONFLICT OF INTEREST POLICY

Any actual conflict of interest of persons who have a role in the design, conduct, analysis, publication, or any aspect of this trial will be disclosed and managed. Furthermore, persons who have a perceived conflict of interest will be required to have such conflicts managed in a way that is appropriate to their participation in the design and conduct of this trial.

10.2 ABBREVIATIONS

AE	Adverse Event
ALP	Alkaline Phosphatase
ALT	Alanine Transaminase
ANCOVA	Analysis of Covariance
ANOVA	Analysis of Variance
ASD	Amorphous Spray Dried Dispersion
AST	Aspartate Aminotransferase
AUC	Area-Under-The-Curve
β-HCG	Human Chorionic Gonadotropin
BMI	Body mass Index
BUN	Blood Urea Nitrogen
CBC	Complete Blood Count
CC	Cubic Centimeter
CFR	Code of Federal Regulations
C _{max}	Maximum (Peak) Concentration
CONSORT	Consolidated Standards of Reporting Trials

COVID-19	Coronavirus Disease 2019
CRF	Case Report Form
CTCAE	Common Terminology Criteria for Adverse Events
CTPA	Computed Tomography Pulmonary Angiogram
DEG	Differentially Expressed Gene
DLT	Dose Limiting Toxicity
DVT	Deep Vein Thrombosis
ECG	Electrocardiogram
eCRF	Electronic Case Report Form
ER β	Estrogen Receptor Beta
FDA	US Food and Drug Administration
FPKM	Fragments Per Kilobase Million
██████████	██████████
GCP	Good Clinical Practice
GLP	Good Laboratory Practice
GMP	Good Manufacturing Practice
g	Gram
HDL	High-Density Lipoprotein
HEENT	Head, Eyes, Ears, Nose and Throat
H/Hr	Hours
IB	Investigator's Brochure
ICF	Informed Consent Form
ICH	International Conference on Harmonisation
██████████	██████████
██████████	██████████
IND	Investigational New Drug Application
INR	International Normalized Ratio Based On PTT
IRB	Institutional Review Board
ITT	Intention-to-Treat
Kg	Kilogram
LAR	Legally Authorized Representative
LBBB	Left Bundle Branch Block
LDPE	Low-Density Polyethylene
LLDPE	Linear Low-Density Polyethylene
M ²	Square Meters
MedDRA	Medical Dictionary for Regulatory Activities
M/F	Male/Female
mg	Milligram
min	Minute
mL	Milliliter
msec	Millisecond
MOP	Manual of Procedures
MTD	Maximum Tolerated Dose
N	Number
NCT	National Clinical Trial

NF-κB	Nuclear Factor Kappa Light-Chain-Enhancer of Activated B Cells
NIH	National Institutes of Health
NF	National Formulary and Drug Standards Laboratory
NYHA	New York Heart Association
OHRP	Office for Human Research Protections
oz	Fluid Ounce
PD	Pharmacodynamics
PI	Principal Investigator
PK	Pharmacokinetics
PTT	Prothrombin Time
PVC	Premature Ventricular Contractions
QC	Quality Control
QTc	Corrected QT Interval
QTcF	QTc with Fridericia's Correction
RBC	Red Blood Cells
RNA	Ribonucleic Acid
SAD	Single Ascending Dose
SAE	Serious Adverse Event
SD	Standard Deviation
SoA	Schedule of Assessments
SOP	Standard Operating Procedure
T _{1/2}	Half-life
TBD	To Be Determined
T _{max}	Time to Reach C _{max}
UP	Unanticipated Problems
USP	United States Pharmacopeia
VTE	Venous Thromboembolism
w	Weight
WBC	White Blood Cells
Yrs	Years

10.3 PROTOCOL AMENDMENT HISTORY

The table below is intended to capture changes of IRB-approved versions of the protocol, including a description of the change and rationale. A Summary of Changes table for the current amendment is located in the Protocol Title Page.

Version	Date	Description of Change	Brief Rationale
0.5	17Sep2020	Initial Release	Initial Release
1.0	16Nov2020	Changed the biomarkers of interest, time period and frequency of AE reporting and reporting of pregnancy	Revised to include acute radiation syndrome relevant biomarkers, provide consistency with the Schedule Activities,

			and remove unnecessary language.
2.0	16Mar2021	Changed the blood draw times for PD (biomarkers) on day 6 of the multiple single dose study Added a pregnancy test to day 1 of the Multiple Single Dose Study Cohort	The original blood draw times were based on the predicted Cmax of BIO 300 Oral Powder from animal studies. The updated blood draw times are based on the actual Cmax from all 4 cohorts in the SAD study conducted under this protocol. Pregnancy test added to day 1 of the Multiple Single Dose Study Cohort to align with inclusion criteria requiring a negative pregnancy test within 72 hours of day 1.

Investigational Agent: BIO 300 Oral Powder

Phase of Development: Phase 1

Sponsor: Humanetics Corporation

Design: Open label, single site phase 1 study in healthy volunteers who are equally distributed by sex. The study will include a single ascending dose (SAD) study in four cohorts and will be followed by a six-day multiple single dose (MSD) study at either the highest dose or the maximum tolerated dose. There are no planned stratifications or sub-studies.

This Statistical Analysis Plan (SAP) details the planned methods for summarizing data collected in the clinical study conducted under Humanetics Corporation protocol CL0106-01. The current study protocol is identified as version 1.0 dated 16-Nov-2020.

Future protocol amendments (if any) will be reviewed to assess whether the changes necessitate modification of this SAP.

Since the study protocol is a companion document to this SAP, aspects in the protocol unrelated to statistical issues (e.g., patient eligibility criteria and detailed BIO 300 Oral Powder information) are not repeated here.

2. Study Objectives

2.1. Primary Objectives

- Determine the overall adverse event and pharmacokinetic (PK) profiles of single ascending doses of BIO 300 Oral Powder in healthy volunteers
- Determine the overall adverse event and PK profile of multiple doses of BIO 300 Oral Powder in healthy volunteers

2.2 Secondary Objectives

- Determine the effects of single and multiple doses of BIO 300 Oral Powder on blood-based biomarkers
- Use a combination of the PK and pharmacodynamic (PD) profiles from the single and multiple doses of BIO 300 Oral powder to identify the putative BIO 300 Oral Powder human efficacious dose

3. Study Endpoints

3.1. Primary Endpoint

- Evaluate the safety and pharmacokinetics of BIO 300 Oral Powder in Healthy Volunteers

3.2. Secondary Endpoint

- Characterize the expression of blood-based biomarkers

4. Sample Size

- 6 subjects/cohort (3M/3F) will be recruited for the single ascending dose study, and at least 6 (3M/3F) subjects/cohort will complete all aspects of the study. 2 additional subjects (1M/1F), will be screened, consented and available as backups for each cohort.
- 10 (5M/5F) subjects will be recruited for the multiple single dose study, and at least 8 (4M/4F) subjects will complete all aspects of the study. 4 additional subjects (2M/2F) will be screened, consented and available as backups.
- In total, at least 32 healthy volunteers who will complete all aspects of the trial.

The single ascending dose study consists of 4 cohorts, each with at least 6 subjects completing all aspects of the study, split evenly to include at least 3 females and 3 males. As such, 12 females and 12 males will participate for a total of 24 subjects. The multiple single dose study will include at least 8 subjects completing all aspects of the study, split evenly to include at least 4 females and 4 males. This is a sufficient number of subjects in each study to characterize the PK and PD of BIO 300 Oral Powder and to identify dose limiting toxicities (DLTs).

5. Analysis Populations

5.1. Intention-to-Treat Analysis Dataset

The Intention-to-Treat (ITT) analysis dataset will include all study participants

5.2. Safety Analysis Dataset

All study participants who receive at least one dose of BIO 300 Oral Powder. This analysis set will be used to summarize all safety endpoints.

5.3. Pharmacokinetic (PK) Population

The PK Population will include all subjects who receive at least 1 dose of BIO 300 Oral Powder and have sufficient, valid serum samples to estimate key parameters for at least 1 of the days of sampling. PK summaries will be based on the PK population.

5.4. Pharmacodynamics (PD) Population

The PD Population will include all subjects who receive at least 1 dose of BIO 300 Oral Powder and have sufficient, valid serum samples to estimate key parameters for at least 1 of the days of sampling. PD summaries will be based on the PD population.

6. Safety Monitoring Committee

A Safety Monitoring Committee (SMC) will review safety and PK data (when available) during the conduct of the study. After each cohort in the SAD study, the SMC will make decisions on proceeding with dose escalation, adding additional subjects to the current cohort, and possible dose adjustments. The SMC may also recommend stopping the study, suspending enrollment or significant changes to the dosing regimen and/or enrollment if warranted by safety data. The SMC will immediately communicate this recommendation to Humanetics for review and determination of a final decision. SMC data reviews are

not considered interim analyses and do not necessitate adjusting of the alpha level for multiple statistical hypothesis tests.

7. Statistical Methods

Unless stated otherwise, the term “descriptive statistics” refers to the number of subjects (n), mean, median, standard deviation (STD), minimum (min), and maximum (max) and standard errors/confidence intervals for continuous response variables and distribution tables or histograms for discrete response variables. Min and max values will be rounded to the precision of the original value, means and medians will be rounded to 1 decimal place greater than the precision of the original value, and STDs will be rounded to 2 decimal places greater than the precision of the original value. Percentages will be rounded to the nearest whole number (zeros are not displayed) with values of “< 1%” and “> 99%” shown as necessary for values falling near the boundaries.

The computed change from baseline will be calculated for all measured variables and expressed as the mean change from baseline + STD of the change from baseline. Analysis of covariance will be used to compare dosage groups on “change from baseline” measures (with baseline measurement considered as an adjustment covariate).

Unless otherwise note, all data collected during the study will be included in data listings and will be sorted by study cohort, subject number and then by visit for each subject number.

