8 STUDY ASSESSMENTS AND PROCEDURES

8.1 CRITERIA FOR EVALUATION

Safety:

The safety profile of BIO 300 Oral Powder will be based on the results of CBC with differential, coagulation parameters, serum chemistries, urinalysis, ECGs, and vital signs the reporting of adverse events.

Pharmacokinetics:

Blood samples will be collected at multiple timepoints after BIO 300 Oral Powder administration and processed for serum isolation. Serum concentrations of genistein aglycone will be measured from PK parameters (C_{max} , T_{max} , clearance, $AUC_{(0-24;0-48;0-INF)}$, volume of distribution, $T_{1/2}$ and drug accumulation index) which will be calculated using standard procedures and statistical analyses.

Pharmacodynamics:

Blood samples will be collected at multiple timepoints in PAXgene tubes after BIO 300 Oral Powder administration. It will be subjected to RNA sequencing to explore biomarkers which may be predictive of BIO 300 Oral Powder effectiveness.

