8.3 BLOOD SAMPLING FOR PHARMACOKINETICS, SAFETY AND BIOMARKERS

Blood will be collected from all subjects to monitor BIO 300 Oral Powder pharmacokinetics, safety, and biomarkers. At each visit where blood sampling occurs, whole blood and serum may be collected for pharmacokinetics, complete blood counts (CBC) with differential, serum chemistry, clotting (PT/INR, PTT) and RNA extraction. A summary of blood draws for safety and biomarkers can be found in **Section 1.3 Schedule of Activities**. Below is an overview of the details of the blood collection summarized by visit.

For blood draws, whole blood will be collected in one 3 cc lavender top blood collection tubes for CBC analysis and two PAXgene blood RNA tubes for RNA isolation. The PAXgene tubes will be stored at -70°C until they are shipped to a Sponsor-designated laboratory for RNA extraction and processing. Blood will also be collected in one 3.5 mL SST collection tube for serum isolation to be used for serum chemistry and 1x 3cc red top blood collection tube for serum isolation to be used for BIO 300 Oral Powder PK analysis. Blood used for serum will be allowed to clot 20-30 minutes and then centrifuged at room temperature for 10-15 minutes. Collected serum will be frozen at -70°C. All blood and serum will be shipped to the sponsor-designated bioanalytical lab for analysis. Additionally, at screening, blood will be collected into another 3.5 mL SST collection tube, and a 3 mL EDTA collection tube to be used for viral testing. Specific blood draw volume requirements for the procedures listed below are detailed in **Section 8.3.1** and **Section 8.3.2**.

Single Ascending Dose

Visit 1 (Screening)

At the screening visit, blood will be collected to acquire the subject's baseline blood counts and serum chemistries, and for viral testing. If a pregnancy test is required for the subject, either a serum or urine test will be done at this time. These test results will assist in determining the subject's ability to be included in the trial (see **Section 5.1 Inclusion Criteria**).

Visit 2 (Day 1)

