9.3. Analysis for Blood-Based Biomarkers

Blood-based biomarkers will be identified by extracting RNA from whole blood samples and performing transcriptome analysis to determine differential gene expression. Transcriptome analysis will be conducted by paired-end RNA sequencing. After investigating the quality of the raw sequencing data, sequence reads will be trimmed to remove possible adapter sequences and nucleotides with poor quality using Trimmomatic v.0.36. The trimmed reads will be mapped to the Homo sapiens reference genome available on ENSEMBL using the STAR aligner v.2.5.2b. The STAR aligner is a splice aligner that detects splice junctions and incorporates them to help align the entire read sequences. Binary Alignment Map (BAM) files will be generated as a result of this step. Unique gene hit counts will be calculated by using feature counts from the Subread package v.1.5.2. Only unique reads that fell within exon regions will be counted.

After extraction of gene hit counts, the gene hit counts table will be used for downstream differential expression analysis. Using DESeq2, a comparison of gene expression between the groups of samples will be performed. The Wald test will be used to generate p-values and Log2 fold changes. Genes with adjusted p-values < 0.05 and absolute log2 fold changes > 1 will be called as differentially expressed genes for each comparison. A gene ontology analysis will be performed on the statistically significant set of genes by implementing the software GeneSCF. The goa_human GO list will be used to cluster the set of genes based on their biological process and determine their statistical significance. A principal component analysis (PCA) will be performed using the "plotPCA" function within the DESeq2 R package. This plot will show the samples in a 2D plane spanned by their first two principal components. The top 500 genes, selected by highest row variance, will be used to generate the plot.

10. Safety Analyses

Summaries of safety endpoints will include data collected from the safety analysis dataset. Relevant data supporting safety analyses will be listed by subject.

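### SAP 5.4 selects the PD population on valid serum samples, but PD is measured only in whole-blood RNA, so the set can leave out usable RNA subjects and count subjects who have none

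*Combined protocol and SAP*

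**What the plan says.** SAP 5.4 defines the PD set: "The PD Population will include all subjects who receive at least 1 dose of BIO 300 Oral Powder and have sufficient, valid serum samples". The sentence goes on to require that the samples allow key parameters to be estimated on at least one sampling day. The rule is operative: "PD summaries will be based on the PD population".

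SAP 5.3 defines the PK set in the same terms: "The PK Population will include all subjects who receive at least 1 dose of BIO 300 Oral Powder and have sufficient, valid serum samples".

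The PD measurement is described differently wherever it appears:

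- Protocol 8.1: "Blood samples will be collected at multiple timepoints in PAXgene tubes after BIO 300 Oral Powder administration".
- Protocol 8.3 separates the tubes. PD has "two PAXgene blood RNA tubes for RNA isolation"; PK has "1x 3cc red top blood collection tube for serum isolation to be used for BIO 300 Oral Powder PK analysis".
- SAP 9.3: "Blood-based biomarkers will be identified by extracting RNA from whole blood samples and performing transcriptome analysis to determine differential gene expression".

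Two other rules bear on the point. The opening of SAP section 9 says that every observation in the database enters endpoint analysis. SAP 7.1 equates baseline with the screening visit.

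**The concern.** An analysis set for an endpoint should be defined by whether that endpoint can be measured. Here, entry to the set for the secondary endpoint depends on a different specimen, collected for a different assay. The phrase about estimating key parameters fits Cmax, AUC and half-life in SAP 9.2. It has no counterpart in the RNA-sequencing analysis of SAP 9.3. The likeliest explanation is that the PK definition was copied.

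The PD results have a real use. Protocol 9.4.3 looks for dose-response in gene expression, and a secondary objective combines PK and PD to identify a presumed effective human dose. If loss from the PD set were tied to low genistein concentrations, the subjects removed would not be a random subset for either purpose. The cohorts are small enough for one subject to matter.

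**Working it through.** **1. The plan's own count.** SAP section 4 gives 4 SAD cohorts of at least 6 completers and one MSD cohort of at least 8: 4 × 6 + 8 = 32. This reproduces the stated 32. The point disputes no figure in the plan.

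**2. Are the specimens distinct?** The blood-volume tables (Protocol 8.3.1 and 8.3.2) list PK serum and PD RNA on separate rows.

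| | PK serum draws | PD RNA draws |
|---|---|---|
| SAD, per subject | 8 + 1 + 1 = 10 (30 mL at 3 mL) | 4 + 1 = 5 (25 mL at 5 mL) |
| MSD, per subject | 5 + 8 + 1 + 1 = 15 (45 mL at 3 mL) | 4 + 4 + 1 = 9 (45 mL at 5 mL) |

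Every RNA visit (SAD Days 1 and 2; MSD Days 1, 6 and 7) is also a serum visit. SAD Day 3 and MSD Day 8 have PK serum and no RNA. The documents describe no PD measurement in serum.

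**3. What the literal rule does.**

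- *Usable RNA, inadequate serum:* excluded. For a SAD subject the serum profile must be inadequate. For an MSD subject both the Day 1 profile (5 samples) and the Day 6 profile (8 + 1 + 1 = 10 samples) must be. SAP 9.2 bars AUC when fewer than 3 concentrations are quantifiable, with values below 1.0 ng/mL set to zero. If AUC is a key parameter, a SAD subject with at most 2 quantifiable values out of 10 could be dropped from PD because exposure was low. SAP 5.4 does not say which parameters are key.
- *Usable serum, no usable RNA:* admitted. The subject has no gene counts to enter DESeq2, and SAP 7.2 does not impute. The PD n is too high; the expression results do not change.

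**4. Which RNA sample is the baseline?** Protocol 9.4.3 plans comparisons relative to baseline within subjects and also comparisons between cohorts. SAP 7.1 puts baseline at screening, but the schedule in Protocol 1.3 has no PD draw there. The Day 1 pre-dose draw (note 14) is the only RNA taken before any dose. SAP 5.4 mentions neither.

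**5. Size of one exclusion.** 1/6 = 16.7% of a SAD cohort; 1/8 = 12.5% of the minimum MSD completers (1/10 = 10% of the planned 10 MSD recruits); 1/32 = 3.1% overall. With the SD unchanged, the standard error of a cohort mean rises by √(6/5) = 1.095 or √(8/7) = 1.069, so by about 10% or 7%.

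**6. How often?** The documents give no rate at which serum and RNA validity differ. As an illustration only, let d be an assumed share of subjects for whom they differ in either direction. The chance of at least one among 32 is 1 − (1 − d)^32.

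| Assumed d | Chance of at least one in 32 | Expected number (32 × d) |
|---|---|---|
| 1% | 28% | 0.3 |
| 2% | 48% | 0.6 |
| 5% | 81% | 1.6 |
| 10% | 97% | 3.2 |

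These values pool both directions, including the one that only inflates n, so they overstate the chance of a wrongful exclusion.

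**The case against.** The strongest reply is that this is a copying slip with little practical effect.

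- Wrongful inclusion adds no expression data. *This stands:* the harm is a misstated n.
- Wrongful exclusion needs inadequate serum on every sampling day while RNA stays usable. Serum is drawn many times, at the same visits as RNA, and Protocol 7.4 makes a subject who misses a timed-draw visit replaceable. *This stands as a limit on likelihood.* It does not cover samples that fail in handling or assay, or a serum profile with too few quantifiable values.
- The opening of SAP section 9 takes in all observations, and Protocol 9.3 makes ITT the primary dataset, so valid RNA might be analysed whatever SAP 5.4 says. *This stands in part.* It is one fair reading, but SAP 5.4 ties PD summaries to its own set, and nothing says which rule prevails. Two conflicting rules leave the choice to be made after the data are in, in an open-label study.

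A reader might infer that the wrong subjects are in fact in or out of the PD analysis, or that one wrong inclusion distorts a large part of the data. The documents support neither. They show a rule that can misclassify, give no failure rates, and leave a wrongly included subject with nothing to contribute. A reader might also infer that anyone without pre-dose RNA should be barred from the set. That goes too far: the between-cohort comparisons in Protocol 9.4.3 can use post-dose samples alone, and SAP 9.3 states no paired model.

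**Conclusion.** The PD population rule is wrong as written and should be corrected. That rests on the text alone and needs no assumption.

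The consequence is conditional. The rule can remove a subject with usable RNA, and it can overstate the PD n. How many subjects this touches is unknown and may be none. If one is removed, the loss is 16.7% of a SAD cohort or 12.5% of the minimum MSD completers. The possible link to low exposure holds only if AUC counts as a key parameter. Only the secondary endpoint and its use alongside PK are affected.

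**What to change.** 1. In SAP 5.4, replace the serum criterion with: at least one dose of study drug and at least one valid post-dose whole-blood RNA sample that passes sequencing quality control. State the pass criteria; SAP 9.3 describes quality review and read trimming but gives no threshold for accepting a sample.
2. Require a valid Day 1 pre-dose RNA sample only for comparisons relative to baseline. State that this sample is the RNA baseline, as an exception to SAP 7.1, because no RNA is drawn at screening.
3. Say how SAP 5.4 and the opening rule of SAP section 9 fit together, for example that all RNA observations from subjects in the redefined PD set are analysed.

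The cost is a few sentences in the SAP and agreement on the quality criteria, with no new samples or visits. The protocol synopsis holds PD samples until all phase 1 studies are complete, so the edit can be made before sequencing data exist. Applying the pre-dose requirement only where it is needed avoids discarding post-dose samples that remain usable between cohorts.
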